8. RESEARCH QUESTION AND OBJECTIVES

8.1 RESEARCH QUESTION

To assess and characterize the frequency of maternal, fetal, and infant outcomes among women with MS exposed to ocrelizumab during the 6 months before the estimated date of conception or at any time during pregnancy.

8.2 OBJECTIVES

The objectives for this registry are as follows:

- To estimate the frequency of selected adverse pregnancy outcomes (i.e., spontaneous abortions, stillbirths, elective or therapeutic terminations, and preterm

births) in women with MS exposed to ocrelizumab during the defined exposure window

- To estimate the frequency of selected adverse fetal/neonatal/infant outcomes (i.e., major and minor congenital malformations, small for gestational age, postnatal growth and development, and outcomes related to immune suppression) at birth and through at least the first year of life of infants from pregnancies in women with MS exposed to ocrelizumab during the defined exposure window
- To compare the maternal, fetal, and infant outcomes of women with MS exposed to ocrelizumab with two unexposed control populations: one consisting of women with MS who have not been exposed to ocrelizumab before or during pregnancy and the other consisting of women without MS

9. RESEARCH METHODS

9.1 STUDY DESIGN

The design of the pregnancy exposure registry is consistent with relevant guidelines and recommendations ([FDA 2002](#); [European Medicines Agency 2005](#); [Gliklich et al. 2014](#); [Andrews et al. 2008](#)). This prospective observational registry will collect primary data from 290 ocrelizumab-exposed pregnant women (153 pregnancy outcomes) with MS and their healthcare providers (HCPs) from the United States, Germany, and other potential countries (see [Section 9.5](#)). Patients who have been exposed to ocrelizumab during the 6 months prior to their last menstrual period (LMP) or at any time during pregnancy are eligible for the ocrelizumab-exposed study group. Inclusion of exposures prior to LMP is based on the half-life and standard of care infusion schedule of ocrelizumab. Dosing and treatment duration of ocrelizumab as part of this non-interventional study are at the discretion of the physician in accordance with local clinical practice and local labeling.

The internal comparator group will consist of currently pregnant women with MS who were not exposed to any MS disease-modifying therapies (DMTs) during the 6 months prior to their LMP or at any time during pregnancy (apart from glatiramer acetate [e.g., Copaxone] exposure through the first trimester (for description and rationale, see [Section 9.7.2.1](#)). Internal comparator patients will be enrolled from the same sites as the ocrelizumab-exposed women and follow the same study procedures for follow-up and data collection. Women will be eligible in the internal comparator group if they fall into one of the following categories:

- Pregnant women with MS with documentation that the patient was not exposed to any MS DMTs during the 6 months prior to their LMP or at any time during their pregnancy
- OR
- Pregnant women with MS with documentation that the patient was exposed to glatiramer acetate during the 6 months prior to their LMP through the first trimester

Major congenital malformations are the primary outcome of interest for this study, and other outcomes are classified as secondary. Data on risk factors, ocrelizumab exposure (among the exposed group), glatiramer acetate exposure (among the comparator group), other therapeutic or environmental exposures, and adverse maternal, fetal, and infant outcomes will be collected from patients and their HCPs (e.g., neurologist, obstetrician) during pregnancy and through at least 1 year after birth (infant's HCP and/or the patient). Congenital malformations will be classified according to the EUROCAT classification system.

The frequencies of outcomes will be presented in comparison to both existing databases and an internal comparator group.

The study is voluntary and exposure to ocrelizumab or glatiramer acetate (e.g., Copaxone) during the study period will be according to national labeling and local standard of care. Any currently pregnant woman with MS exposed to ocrelizumab (exposed group) or pregnant woman with MS not exposed to any MS DMTs or only exposed to glatiramer acetate, as defined above, will be eligible for the study. The total duration of participation is up to 21 months and the total expected duration of the study is approximately 10 years.

9.1.1 Registry Recruitment and Retention

Complete details of registry awareness, outreach, and retention efforts will be described in the Recruitment and Retention Plan, and may include the following methods to (1) increase awareness of the registry by using multiple approaches aimed toward HCPs and patients, such as websites, social media, print media, and scientific conferences; (2) evaluate awareness of the registry periodically; (3) accept data from multiple sources; (4) minimize the burden on HCPs; (5) ongoing communications with HCPs and patients; (6) possible compensation for HCPs; and (7) minimize the burden on subjects. Compensation will be considered for patients and/or HCPs where allowed by local regulations. All activities in this plan will be reviewed on a regular basis. The Recruitment and Retention Plan will be submitted for FDA review and approval.

9.1.1.1 Registry Awareness

The registry will utilize awareness strategies that have appeared to be effective in other pregnancy exposure registry programs. Increased awareness of the registry will use multiple approaches aimed towards both HCPs and patients, such as social media, paper and electronic media, and scientific conferences. Registry awareness activities and content will be evaluated on a regular basis to ensure target populations are being reached yet minimize any burden on the recipients. Channels for providing feedback on Registry material and corresponding with potential HCPs and patients will be detailed in the Recruitment and Retention Plan.

9.1.1.2 Outreach Efforts

Active outreach will occur to obtain reports of women with MS who are exposed to ocrelizumab during pregnancy, as well as women with MS who are eligible for the internal comparator who receive medical care from the same clinical sites. Outreach efforts may include the following:

- Discussion of the Registry with investigators participating in ocrelizumab clinical studies, with periodic written reminders
- Collaboration with investigators of independent MS pregnancy registries
- Notification of the Registry to neurologists and other practitioners who may prescribe ocrelizumab, as well as MS education and support groups, via the following:
 - E.U. Post-Authorization Study (PAS) Register
 - Ocrelizumab Pregnancy Registry website
 - Investigator awareness electronic flyer
 - Investigator referral letters
 - HCP introduction letters

Recruitment of patients is dependent on several factors: Uptake of new medications such as ocrelizumab is unpredictable and has the potential to impact the feasibility of meeting the recruitment targets in the United States and Germany. In addition, the expected pace of exposure to pregnant women and the willingness of pregnant women (both ocrelizumab-exposed and internal comparator groups) to participate in a registry are both difficult to predict. Continuous monitoring of patient recruitment (comparing projections and observed rates) will allow for strategies to be employed in response to any recruitment challenges.

9.1.1.3 Retention Efforts

Registry retention efforts will include (but not be limited to): general study eNewsletters to HCPs and an optional (opt-in) communications program that includes: engagement e-mails, SMS/e-mail/Call reminders, and thank-you messages for patients and SMS/e-mail/call reminders for HCPs. Compensation will be issued (where allowed by local regulations) to all patients and/or HCPs who enroll in the communications program. As detailed in *FDA Guidance for Industry: Establishing Pregnancy Exposure Registries, Section IX*, study design and approach, and factors for determining if a registry should continue will be routinely evaluated ([FDA 2002](#)). The projected versus observed drop-out rates will be continuously monitored. Retention planning will be performed in advance as part of the Recruitment Risk Management with triggers for implementation of actions identified, as well as steps to take if the rate of patient completion decreases. Retention efforts for both HCPs and the patients will be documented in the Recruitment and Retention Plan. Steps to ensure recruitment and retention of patients in the Registry include actions for implementation at study start, in addition to actions that

could be implemented as the study progresses and new enrollment information becomes available.

9.1.2 Start Date of Study

The study start date will be the date of the first data collection: the date from which information on the first study patient is recorded in the study database.

9.1.3 End of Study

The end of the study will be the date from which the last data collected from the last subject is recorded in the study database. A data collection overview is provided in [Appendix 2](#).

9.2 SETTING

HCPs who treat patients with MS including investigators involved in ongoing or future clinical studies of ocrelizumab will be informed of the study and asked to refer any patient who becomes pregnant to the appropriate study coordinating center (CC). Reporting of pregnancy exposures to ocrelizumab is voluntary and pregnancies should be reported as early as possible, ideally before prenatal testing has been performed. The same model will be used for referring and reporting pregnancies for the internal comparator group. Pregnancies with known outcomes (i.e., pregnancy loss or live birth) at the time of the initial report will not be included in the study but will be followed by Roche according to standard postmarketing pharmacovigilance.

9.2.1 Centers

This study will be conducted in Germany and the United States, and potentially in other countries. Each country will have at least one CC that is responsible for obtaining informed consent and all patient and HCP contacts during the study.

9.2.2 Study Population

Pregnant patients may be enrolled prospectively from the postmarketing setting or other clinical or observational studies of ocrelizumab. In order to reduce bias that may occur if outcome information is known prior to enrollment, women should be enrolled in the study as soon as their pregnancy is known, preferably in the first trimester.

Women who have had prenatal testing prior to enrollment that could determine the status of the fetus (e.g., amniocentesis, genetic testing, nuchal translucency screen, chorionic villus sampling, and late term ultrasound) will still be considered prospective cases. However, the primary data analysis will exclude women who have received first trimester prenatal screening, in which either aneuploid disorders or genetic disorders that cause major congenital malformations have been detected. Retrospective cases are women where the pregnancy outcome is known, prior to enrollment in the registry, either positive or negative, for major congenital malformations that are unrelated to

genetic or aneuploid disorders. Retrospective cases will be analyzed separately for both primary and secondary analysis.

No exclusion criteria will apply for this study.

9.2.2.1 Ocrelizumab-Exposed

To be eligible to participate in the ocrelizumab-exposed study group, patients must meet the following criteria prior to study entry:

- Patient consent (written or verbal per local regulations or Ethics Committee requirements) obtained prior to enrollment. If the patient is a minor, written consent must be obtained from their parent or legal guardian. Consent will be obtained in compliance with any country-specific regulations or requirements.
- Currently pregnant
- Diagnosed with MS
- Documentation that the patient was exposed to ocrelizumab at any point starting from 6 months prior to LMP
- Agrees to sign the Release of Medical Information Form permitting the study to contact her HCP(s) and the pediatric HCP for medical information
- The outcome of the pregnancy (i.e., pregnancy loss or live birth) must not be known.

9.2.2.2 Internal Comparator

To be eligible to participate in the internal comparator group, patients must meet the following criteria prior to entry:

- Patient consent (written or verbal per local regulations or Ethics Committee requirements) obtained prior to enrollment. If the patient is a minor, written consent must be obtained from their parent or legal guardian. Consent will be obtained in compliance with any country-specific regulations or requirements.
- Currently pregnant
- Diagnosed with MS
- Documentation of one of the following:
 - Pregnant women with MS who were not exposed to any DMTs during the 6 months prior to their LMP or at any time during their pregnancy
 - OR
 - Pregnant women with MS who were exposed to glatiramer acetate during the 6 months prior to their LMP through the first trimester
- Agrees to sign the Release of Medical Information Form permitting the study to contact her HCP(s) and the pediatric HCP for medical information
- The outcome of the pregnancy (i.e., pregnancy loss or live birth) must not be known.

The rationale for glatiramer acetate exposure in the internal comparator is summarized in [Section 9.7.2](#).

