- Indirectly due to known or unknown infections or infectious complications in the mother exposed to ocrelizumab during pregnancy, which may affect the offspring, where the infection may be associated with ocrelizumab exposure
- Indirectly due to effects of ocrelizumab on the placenta

Based on the average ocrelizumab terminal half-life of 26 days reported in the studies of MS (Genentech Inc. 2017), it is expected that ocrelizumab would be eliminated from the body approximately 4.5 months after the last administration. Considering the interpatient variability (the longest terminal half-life recorded in women was 53 days) and the absence of placental transfer of immunoglobulins during the first trimester of pregnancy, it is recommended that women of childbearing potential should use contraception while receiving ocrelizumab and for 6 months after the last infusion of ocrelizumab. However, women may get pregnant during this period due to noncompliance with contraception or failure of contraceptive methods.

Clinical studies of the effects on pregnancy and offspring associated with the use of ocrelizumab during pregnancy, during lactation, and/or before conception have not been performed, and experience from ocrelizumab clinical trials is limited. As of 31 January

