9.5 STUDY SIZE

The sample size for this study was calculated based on clinical, statistical, and practical considerations to determine the number of enrolled patients with pregnancies required to detect the prevalence of adverse pregnancy outcomes in the study and associated relative risk. Major congenital malformations are the primary outcome of interest for this study, and other outcomes are classified as secondary.

Assuming a 15% drop-out rate and a live birth rate of 62% ([FDA 2002](#); [Ventura et al. 2000](#)), 290 ocrelizumab-exposed pregnant women with MS will need to be enrolled to observe 153 pregnancy outcomes. This sample size provides 80% power to detect a relative risk of 2.5 or greater in major congenital malformations relative to the baseline prevalence of 3% in the external comparator ([CDC 2008](#)) at a significance level of $\alpha=0.05$ ([Table 2](#)). Should the actual live birth rate exceed 62%, fewer enrolled pregnant patients would be necessary to adequately power this study.

[Table 3](#) shows point estimates and 95% CIs for different hypothetical numbers of observed cases. With 153 pregnancy outcomes, an observed number of 14 major congenital malformations will give an estimated prevalence of 9% with 95% CI of (5.0%-14.7%), rejecting a relative risk of 1 when the baseline prevalence is 3%. Likewise, 18 major birth defects and 46 preterm births will reject a relative risk of 1 when the baseline prevalence is 4% and 10%, respectively.

In addition to the external comparator, the internal comparator group will enroll approximately 290 pregnant women to support the study objective to compare the maternal, fetal, and infant outcomes of women with MS who have not been exposed to

ocrelizumab before or during pregnancy. The internal comparator will provide supportive evidence to the comparison with the external comparator.

Table 2 Sample Size of Pregnancy Enrollment (Outcome) for 80% Power

Relative Risks	Number of Patients Exposed to Ocrelizumab for a Single Proportion Test when Comparing with an External Comparator	Number of Patients Exposed to Ocrelizumab for a Two Proportions Test when Comparing with an Internal Comparator with a 1:1 Allocation Ratio
2.0	602 (Pregnancy outcomes needed: 317)	1489 (Pregnancy outcomes needed: 785)
2.5	290 (Pregnancy outcomes needed: 153)	793 (Pregnancy outcomes needed: 418)

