	Caffeine consumption	Y/N; if yes, how many caffeinated beverages (e.g., coffee) per day over the last week?
	Alcohol consumption	Drinks/week
	Illicit drug use	Y/N, then choose type of illicit drug
Current Pregnancy	Date of LMP	Calendar provided to help recall
	EDD	Calendar provided to help recall

Variable Category	Data Elements	Additional Information
	Date and results of any prenatal testing	Calendar provided to help recall rubella titer, toxoplasmosis, venereal disease, hepatitis, ultrasounds, amniocentesis, maternal serum alpha-fetoprotein, glucose
Medical History		
Pregnancy History	Parity	
	Gravidity	
	Previous preterm births	
	Previous spontaneous abortions	
	Previous elective or therapeutic terminations (and reason, if any given)	
	History of any congenital malformations	
	Other (please specify)	Free text field (e.g., neonatal sepsis, birth trauma and birth asphyxia)
Surgical History	Past surgical procedures and date(s)	Any
Medical Conditions (other than MS)	(e.g. Diabetes, high blood pressure, malignancy)	
	Diagnosis	
	Start date(s)	
	End date(s)	
	Disease duration (calculated field)	
MS Disease	Date of first MS symptom	
	Diagnosis date	
	Date of most recent relapse	Or patient did not have any relapses. If yes, Total number of relapses experienced within the past 12 months, 2 years, and 3 years
	MS subtype	
	Disease duration (calculated field)	

Variable Category	Data Elements	Additional Information
	EDSS score (if available)	
Prior MS Treatment	Drug name	Multiple entries allowed
	Start date(s)	
	End date(s)	
	Dose	
	Reason for stopping treatment	
Family Reproductive History	Baby's father/Baby's mother's family/Baby father's family -- ever fathered other pregnancies with any of the following;	Y/N
	Multiple births	
	Congenital malformations	If yes, please specify:
	Spontaneous abortions	
	Premature births	
	Chromosomal anomalies	
	Developmental delays	
Family MS History	Other family members with MS (mother, father, other)	If yes, please specify which family member
	MS type	
	Age at diagnosis	
Ocrelizumab Treatment	Start date(s)	
	End date(s)	
	Dose	
	Dosing frequency	
	Reason for discontinuation (if applicable)	
	Duration of use (calculated field)	
Prior and Current Medications (all medications used from 6 months prior to LMP such as glatiramer	Name of medication	Multiple entries allowed
	Indication	
	Start date(s)	

Variable Category	Data Elements	Additional Information
acetate)	End date(s)	
	Dose	

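### Past ocrelizumab users (last infusion more than 6 months before LMP) count as unexposed internal comparators, although objective 3 asks for women not exposed before or during pregnancy

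*Protocol*

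**What the plan says.** Section 8.2 of the protocol describes two control populations for objective 3. The MS one is "one consisting of women with MS who have not been exposed to ocrelizumab before or during pregnancy". The cover page and the synopsis use the same description, and 9.5 repeats it as the purpose of enrolling about 290 comparators.

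The operational definition is narrower. The first branch of 9.2.2.2 takes women with MS "who were not exposed to any DMTs during the 6 months prior to their LMP or at any time during their pregnancy". The synopsis, 9.1, 9.3.1 and Appendix 3 (Table 1) apply the same 6-month look-back. The exposed group in 9.2.2.1 needs "Documentation that the patient was exposed to ocrelizumab at any point starting from 6 months prior to LMP". Section 9.2.2 adds: "No exclusion criteria will apply for this study".

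Section 9.7.1 analyses the comparator overall and in two subgroups, DMT-unexposed and glatiramer-exposed. The same section calculates total duration of ocrelizumab exposure up to 6 months after the stop date. Section 9.1 bases the pre-LMP window on half-life and infusion schedule. Section 7.2 gives an average half-life of 26 days, expects elimination after about 4.5 months, and notes that "the longest terminal half-life recorded in women was 53 days".

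**The concern.** A woman whose last infusion fell more than 6 months before LMP is an unexposed control under the eligibility criteria but was exposed before pregnancy in the plain words of objective 3. Such women are foreseeable: 7.2 cites a recommendation of contraception for 6 months after the last infusion, and 9.7.2.1 recruits comparators from the same centers as exposed women. The protocol names no stratum for them.

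Two things are at stake. The registry would not report the contrast its third objective promises. And if ocrelizumab has any effect that outlasts 6 months, part of it would be counted on the comparator side and the internal risk ratio would be diluted, which in a safety registry is the direction that hides harm.

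**Working it through.** **Step 1. Follow one woman through the protocol.** Take a last infusion 7 months before LMP.

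- 9.2.2.1 (exposed group): exposure counts only from LMP minus 6 months, so she is not eligible.
- 9.2.2.2 (first branch): no DMT since LMP minus 6 months, so she is eligible. No exclusion criterion removes her, and 9.7.2.1 refers back to 9.2.2.2 without adding one.
- 9.7.1 (subgroups): she falls in the DMT-unexposed subgroup.
- 9.7.1 (duration rule): stop date + 6 months = LMP minus 1 month.

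For a last infusion m months before LMP, with m between 6 and 12, the duration rule and the look-back window overlap by 12 − m months. At m = 7 that is 5 of the 6 months.

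**Step 2. Reproduce the protocol's elimination figure.** 4.5 months × 30.44 = 137 days, and 137/26 = 5.3 average half-lives. The same multiple at 53 days is 5.27 × 53 = 279 days, or 9.2 months.

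**Step 3. Residual drug, fraction = 2^(−days/half-life).** The last infusion is taken at 183 days before LMP; week 16 is then day 183 + 112 = 295.

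| Half-life (7.2) | At LMP (day 183) | At week 16 (day 295) |
|---|---|---|
| 26 days (average) | 0.8% | 0.04% |
| 53 days (longest in women) | 9.1% | 2.1% |

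Week 16 matters because 7.2 assumes direct fetal exposure only after that point. Six months covers the average woman; at LMP it does not fully cover the slowest eliminator.

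**Step 4. Dilution of the internal risk ratio.** The protocol gives neither the share of past users (f) nor any lasting effect, so both are assumed. The true RR of 2.5 is the planning value for major malformations in 9.5. With RRpast the risk ratio of past users against never-exposed women:

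observed RR = 2.5 / [(1 − f) + f × RRpast]

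| f | No excess persists (RRpast 1) | Half persists (RRpast 1.75) | All persists (RRpast 2.5) |
|---|---|---|---|
| 10% | 2.50 | 2.5/1.075 = 2.33 | 2.5/1.15 = 2.17 |
| 20% | 2.50 | 2.5/1.15 = 2.17 | 2.5/1.30 = 1.92 |
| 30% | 2.50 | 2.5/1.225 = 2.04 | 2.5/1.45 = 1.72 |

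The last column is an extreme: it gives a woman with little or no drug left the same risk as one within the exposure window.

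**The case against.** The strongest reply is that objective 3 is shorthand. Its exposed half also states no window, yet nobody reads it as ever-exposed; the research question in 8.1 sets 6 months; and under the duration rule in 9.7.1 a woman infused 7 months before LMP is no longer exposed at LMP. That rule summarises duration and does not assign groups. This is a possible reading, but objectives 1 and 2 in the same list refer to the defined exposure window and objective 3 does not, and 9.5 repeats the unlimited wording. The text needs reconciling either way.

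A reader might infer that the half-life figures show 6 months to be an inadequate washout. The protocol does not support that. Section 7.2 reaches 6 months by weighing the 53-day half-life together with the absence of placental transfer in the first trimester, and by week 16 even the slowest recorded woman retains about 2%. For the same reason, nothing shows that infant B-cell or immunoglobulin outcomes would be the most distorted. What remains is narrower: the placental-transfer argument concerns direct fetal exposure, while 7.2 also lists theoretical indirect routes through maternal infection and the placenta.

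It can also be said that a past-user analysis could sit in the SAP, which is not at hand. That holds for the analysis. It does not hold for a mismatch between objective and eligibility, which is protocol content.

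**Conclusion.** The mismatch holds on the text: objective 3 and 9.5 describe controls not exposed before pregnancy, while every operational definition of the DMT-unexposed branch looks back only 6 months before LMP.

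The bias is conditional. It is zero if nothing persists beyond 6 months. Otherwise it moves the internal risk ratio towards 1, in the assumed examples from 2.5 to between 2.33 and 2.04 (half the excess persists, 10-30% past users) or, at the extreme, between 2.17 and 1.72. These are illustrations, not estimates. It would be tempting to say that past users will be common or that the internal risk ratios are in fact diluted, but the protocol gives no share and no evidence of a lasting effect.

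Severity is moderate. Section 9.5 calls the internal comparator supportive, the study size of 290 rests on the external comparison, and neither that comparison nor objectives 1 and 2 are affected.

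**What to change.** 1. Reconcile objective 3 (cover page, synopsis, 8.2) and its repetition in 9.5 with 9.2.2.2, 9.3.1 and the duration rule in 9.7.1, and carry the result into the synopsis criteria, 9.1 and Appendix 3.
2. Derive a flag for past ocrelizumab (last infusion more than 6 months before LMP) from the drug names and dates under "Prior MS Treatment" in Appendix 3, Table 1.
3. Report flagged women as a third comparator stratum beside DMT-unexposed and glatiramer-exposed.
4. Present the internal risk ratios with these women excluded, which is the contrast objective 3 states, and with them included.

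The cost is wording, one derived variable and one extra set of estimates; no new data are needed. The never-exposed contrast will have slightly fewer comparators. They may also have milder MS, which could add to the channeling described in 9.9, so the comparison should be adjusted for the baseline MS severity already collected. Barring all past users from the comparator group is not needed and would lose the chance to look at them.
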